8.5.3. Solicited Events and Symptoms

A solicited AE is a predetermined event, identified in the Investigator's Brochure, which may reflect safety concerns related to the investigational product. The solicited AEs for this study include:

- Redness, swelling, bruising, pain or tenderness at the injection site
- Fever
- Myalgia (general muscle aches)
- Headache
- Lymphadenopathy
- Axillary pain or discomfort
- Tachypnea
- Fatigue

The study analysis will include Solicited AEs occurring from the time of each injection through 14 days following each procedure. Tables 2.3.1 and 2.3.2 will summarize Solicited AEs by the number and percentage of subjects experiencing solicited events by symptom, relationship to study product, treatment group, and maximum severity.

All reported solicited AEs will be provided in Listing 1.11.3.

8.5.4. Unexpected Adverse Events or Unexpected Suspected Adverse Reaction

An adverse event or suspected adverse reaction is considered "unexpected" if it is not listed in the investigator brochure or is not listed at the specificity or severity that has been observed; or, if an investigator brochure is not required or available, is not consistent with the risk information described in the general investigational plan or elsewhere in the current application, as amended. For example, under this definition, hepatic necrosis would be unexpected (by virtue of greater severity) if the investigator brochure referred only to elevated hepatic enzymes or hepatitis.

Similarly, cerebral thromboembolism and cerebral vasculitis would be unexpected (by virtue of greater specificity) if the investigator brochure listed only cerebral vascular accidents.

"Unexpected," as used in this definition, also refers to adverse events or suspected adverse reactions that are mentioned in the investigator brochure as occurring with a class of drugs or as anticipated from the pharmacological properties of the drug, but are not specifically mentioned as occurring with the particular drug under investigation.

8.5.5. Unanticipated Problems Involving Risks to Subjects or Others

Federal regulations require that unanticipated problems involving risks to subjects or others be promptly reported to the IRB. These events encompass a broader category of events than SAEs and may include issues such as problems with loss of control of subject data or the investigational product; adverse psychological reactions; or breach of confidentiality. Risks to others (eg, program personnel) must also be reported.

Unanticipated problems involving risks to subjects or others are any incident, experience, or outcome that meets all of the following criteria:

- Unexpected (in terms of nature, severity, or frequency) given (a) the procedures that are described in the protocol, investigators brochure or informed consent document; and (b) the characteristics of the subject population;
- Related or possibly related to a subject's participation in the study; and
- Suggests that the study places subjects or others at a greater risk of harm than was previously known or recognized.

The PI will determine whether a given incident, experience or outcome constitutes an unanticipated problem involving risk to subjects or others and, in coordination with the sponsor, ensure upward reporting of the unanticipated problems involving risk to subjects or others to the appropriate regulatory offices.

Tables 2.3.3 and 2.3.4 will be created to summarize the incidence and intensity of solicited AEs. The tables will provide the number and percentage of subjects experiencing unexpected adverse events considered unrelated, unlikely, possibly, probably, or definitely related; as well as by MedDRA® System Organ Class, Severity, and Treatment Group.

All reported unexpected AEs or Unexpected Suspected Adverse Reactions will be provided in Listing 1.11.2.

8.6. Serious Adverse Event or Serious Suspected Adverse Reaction

An adverse event or suspected adverse reaction is considered “serious” if, in the view of either the investigator or sponsor, it results in any of the following outcomes:

- Death
- Life-threatening adverse event
- Inpatient hospitalization or prolongation of existing hospitalization
- Persistent or significant incapacity or substantial disruption of the ability to conduct normal life functions
- Congenital anomaly/birth defect

An adverse event or suspected adverse reaction is considered “life-threatening” if, in the view of either the investigator or sponsor, its occurrence places the patient or subject at immediate risk of death. It does not include an adverse event or suspected adverse reaction that, had it occurred in a more severe form, might have caused death.

Important medical events that may not result in death, be life-threatening, or require hospitalization may be considered serious when, based upon appropriate medical judgment, they may jeopardize the patient or subject and may require medical or surgical intervention to prevent one of the outcomes listed in this definition. Examples of such medical events include allergic bronchospasm requiring intensive treatment in an emergency room or at home, blood dyscrasias or convulsions that do not result in inpatient hospitalization, or the development of drug dependency or drug abuse.

All SAEs will be:

- Assessed for severity and relationship to study product and alternate etiology (if not related to study product) by a licensed study physician listed on the Form FDA 1572 as the site principal investigator or sub-investigator Day 1 through Day 220.
- Recorded on the appropriate SAE form and eCRF.
- Followed through resolution or stabilization by a licensed study physician listed on the Form FDA 1572 as the site principal investigator or sub-investigator.
- Reviewed and evaluated by an SMC, RM/ISM, DMID, PSSB PVG physician, and the IRB, if indicated

All reported SAEs will be provided in Listing 1.11.1, which will include treatment group, subject ID, date reported, dose number, body system, MedDRA preferred term, severity grade, intervention, outcome, relationship to study product, and, if not, the etiology.

8.7. Pregnancies

Each pregnancy must be reported immediately (within 24 hours of identification) by email or fax to the USAMRMC ORA PSSB. Report the incident to UMB IRB and/or the USAMRMC ORP in accordance with IRB policy.

Subjects who become pregnant after Day 0 will be followed until 30 days after delivery to determine outcome, including spontaneous or voluntary termination, details of the birth, and the presence or absence of any birth defects, congenital abnormalities, or maternal and/or newborn complications. The following information will be gathered for outcome, date of delivery, health status of the mother and child including the child's gender, height and weight. Complications and or abnormalities should be reported including any premature terminations. A pregnancy is reported as an AE or SAE only when there is suspicion that the investigational product may have interfered with the effectiveness of contraception or there was a serious complication in the pregnancy including a spontaneous abortion or an elective termination for medical rationale, or the infant has a congenital anomaly/birth defect.

8.8. Clinical Laboratory Evaluations

Clinical Safety Laboratory testing will be performed at the following study visits: Screens, 1, 3, 4, 6, 7 and 9. (Listing 1.7)

For hematology and serum chemistry tests, any clinically significant changes from baseline value will be identified and reported.

The median, interquartile range, and normal values for each laboratory values (as determined by the contract laboratory) will be reported for each treatment group for each specimen collection point.

8.9. Vital Signs and Physical Evaluations

Vital sign measurements will be collected at each of the 12 study visits (Listing 1.8). Full or directed Physical Examinations will be performed at each of the 12 study visits (Listing 1.9).

8.10. Concomitant Medications

The only restrictions on the use of concomitant medications by subjects during this study are medications that are presented in protocol section 9.3. Concomitant medication use will be assessed at each study visit and provided in Listing 1.6.

9. IMMUNOGENICITY

Descriptive analysis of immunogenicity outcomes will include all subjects who meet the eligibility criteria, received at least one vaccination, and for whom serological data is available. The primary analysis variable is the proportion of seropositive subjects ($\text{PsVNA50} \geq 1:20$) at each scheduled time point (e.g., Days 0, 28, 56, 84, 140, and 220) (Table 3.1), and the final overall rate of seroconversion over these timepoints. Additionally, the proportion of subjects to ever reach seropositivity will be provided at each scheduled time point for which blood samples are taken (Table 3.2). Duration of seropositivity is presented in Table 3.3. For each study group, a binomial proportion, and corresponding 95% CI will be calculated. Chi-squared test or Fisher's exact test will be used to examine the association between group and each binary outcome of interest. Figures 1.1 and 1.2 will present percentages of subjects with seropositivity and seroconversion, by time point by group.

The secondary analysis variable is geometric mean titers, with 95% CIs, of the PsVNA50 for HTNV and PUUV specific antibodies at each scheduled time point (e.g., Days 0, 28, 56, 84, 140, and 220), and will be presented in Figure 1.5. Geometric mean titers, standard errors, and 95% CIs will be calculated using log-transformed titers, titers below the lower limit of detection (<20) will be transformed to a value equal to the lower limit of detection divided by the square root of 2 ($20/\sqrt{2} = 14.1$ Hornung & Reed (1990) (Table 3.4). PsVNA80 titers may be calculated from existing data for information. The reciprocal of the dilution that results in an 80% decrease in luciferase activity is the PsVNA80 titer. PsVNA using other hantavirus PsV (eg, Seoul virus, Dobrava virus) may also be performed to evaluate levels of cross-neutralizing antibodies. Additionally, Fisher's exact test will be used to examine the difference in the proportion of participants to ever seroconvert between each two groups (Table 4.3).

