6.3. Measures Taken to Minimize/Avoid Bias

6.3.1. Randomization

A randomization plan will be used to allocate subjects into experimental groups, per the study priorities described in Section 6.2. In addition, as of Version 5.0, ten replacement subjects will be enrolled into Group 6. A fixed random allocation will ensure that the groups are balanced in size at the end of experiment.

Designated study personnel (excluding the principal investigator [PI] and other investigators) will fill the vaccine cohorts as potential subjects successfully complete the screening process and are deemed eligible to participate by the PI (or another designated investigator). For the purposes of this study, the groups will be defined as follows, and each subject will receive one dose of vaccine on Days 0, 28, and 56.

Group 1 (12 subjects): HTNV by ID EP

Group 2 (12 subjects): HTNV by IM EP

Group 3 (12 subjects): PUUV by ID EP

Group 4 (12 subjects): PUUV by IM EP

Group 5 (12 subjects): HTNV/PUUV by ID EP

Group 6 (22 subjects): HTNV/PUUV by IM EP

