11.3. Level of Significance to Be Used

All statistical analyses will be made using a two-tailed $\alpha = 0.05$.

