3.2. Secondary Objectives

- To obtain a preliminary assessment of the immunogenicity of the combination HTNV/PUUV DNA vaccine candidate relative to the monovalent formulations.
- To identify the HTNV and/or PUUV DNA vaccine combination and route of administration that elicits the most immunogenic response as determined by seroconversion and seropositivity rates, and geometric mean titers (GMT) as measured by PsVNA50.

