4. INVESTIGATIONAL PLAN

4.1. Overall Study Design

The study design, including doses and schedule, is based on the experience of a team of investigators to include personnel at USAMMDA (now ORA), USAMRIID, Ichor, and WRAIR, who have performed clinical trials with similar DNA vaccine constructs using Ichor's TDS-IM EP device for DNA vaccinations. These TDS-IM and TDS-ID EP devices have been tested in humans previously in a recent clinical trial to evaluate the safety and immunogenicity of a DNA vaccine for Venezuelan encephalitis virus. These same HTNV and PUUV DNA vaccine products have also been tested in humans previously, albeit only using the TDS-IM EP device, and at lower dose levels than proposed in this study. Previous studies examined these vaccines in Phase 1 and 2 clinical trials at up to 2-mg dose levels per IM EP administration, whereas this study is testing up to 6 mg of DNA per administration using the 2 devices. The GLP repeat-dose rabbit toxicology and immunogenicity study performed in support of this study administered these same HTNV and PUUV DNA vaccines at up to 6 mg doses using the 2 devices and at an increased dosing frequency compared to this proposed Phase 1 clinical trial design. The rabbit toxicology study did not reveal safety concerns for the use of this higher dose level and with these 2 devices.

This study will be a single-center, randomized, study of the HTNV, PUUV, and combined HTNV/PUUV DNA vaccines delivered IM and ID by EP.

Pending sentinel group outcomes (elaboration in Section 4.2.1), the study will enroll up to 6 randomized groups of up to 12 subjects each for a total of up to 72 subjects (12 enrolled in effort to ensure at least 10 will complete per group). The HTNV and PUUV DNA vaccines will be administered to subjects as follows:

Group 1: 0.6 mg HTNV by ID EP

Group 2: 3.0 mg HTNV by IM EP

Group 3: 0.6 mg PUUV by ID EP

Group 4: 3.0 mg PUUV by IM EP

Group 5: 1.2 mg HTNV/PUUV by ID EP

Group 6: 6.0 mg HTNV/PUUV by IM EP

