4.3. Study Sample

The study sample will consist of up to 72 healthy male and nonpregnant, nonlactating female subjects, ages 18 to 49 years (inclusive), who are HTNV and PUUV naïve (i.e., up to 12 subjects per group). The intended study sample for the study is 60 participants (i.e., 10 subjects per group). Due to attrition concerns, an additional 2 participants will be enrolled to each group to bring the total study sample to 72. Please refer to Section 5 for details on the relationship between the sample size and expected power of analyses.

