5. SAMPLE SIZE CONSIDERATIONS

Because this is a pilot study, all analyses are exploratory. The group sample sizes of up to 12 subjects thus were chosen without the intention that group differences will be detected with a sufficient power.

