6.7. Multiple Comparisons/Multiplicity

Multiplicity adjustments are not planned.

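### The six-group test in SAP 9 includes groups never given the antigen if outcomes are virus-specific, and isolates neither route nor combination on any reading

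*SAP*

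**What the plan says.** SAP 9 makes seropositivity at each time point and overall seroconversion the primary immunogenicity variables, and adds: "Chi-squared test or Fisher's exact test will be used to examine the association between group and each binary outcome of interest". It names no groups and excludes none. In Appendix I, Table 4.3 has a p-value cell on the row that shows all six groups, above seven pairwise rows.

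Groups 1 and 2 receive HTNV vaccine only. Groups 3 and 4 receive PUUV vaccine only (for example "Group 3: 0.6 mg PUUV by ID EP" in SAP 4.1). Groups 5 and 6 receive both. Under Protocol 9.2 every serum is screened in both assays, so results for both viruses will exist in all six groups.

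The SAP does not say whether the binary outcomes are per virus. SAP 3.4 defines seroconversion by a titre specific to one virus or the other, and Tables 3.1, 3.2 and 4.3 have one column per group with no split by virus. In SAP 9 only the geometric mean titres are described for each virus.

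The question to be answered is in SAP 3.2: "To obtain a preliminary assessment of the immunogenicity of the combination HTNV/PUUV DNA vaccine candidate relative to the monovalent formulations". The companion objective asks which combination and route is most immunogenic. On error control, Protocol 11.3 says "All statistical analyses will be made using a two-tailed" 0.05, and SAP 6.7 says "Multiplicity adjustments are not planned". On size, SAP 5 calls all analyses exploratory and adds: "The group sample sizes of up to 12 subjects thus were chosen without the intention that group differences will be detected with a sufficient power".

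**The concern.** An HTNV-specific outcome compared across all six groups includes two groups that were never given HTNV vaccine, and the same holds for PUUV. The null of equal response is then false by design, whatever the truth about route or combination. A small p-value may say only that subjects not vaccinated against a virus tend not to respond to it.

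The risk is that such a p-value is read as evidence that ID differs from IM, or that the mixture differs from the single vaccines. The exposure is greatest for seropositivity at each time point. The pairwise Fisher tests in SAP 9 are specified only for ever seroconverting, so for seropositivity the all-group test is the only between-group test in the plan.

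**Working it through.** **The plan's own figure.** The documents give no error rate or power for the across-group test. The one related figure, in Protocol 11.2, is that 7 of 10 seroconverters establish a rate of at least 30%. It reproduces: the two-sided exact 95% lower bound is 34.8% for 7/10 and 26.2% for 6/10. It does not concern group comparisons.

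**Inputs.**
- Two-sided level 0.05 (Protocol 11.3), no multiplicity adjustment (SAP 6.7).
- Group sizes: 10 (intended completers, SAP 4.3), 12 (SAP 5), or 12 in Groups 1 to 5 and 22 in Group 6 ("Group 6 (22 subjects): HTNV/PUUV by IM EP", Protocol 6.3.1).
- Response p in groups given the antigen: 44% to 78%, the range in Protocol 4.4.2.1.1. Those rates come from an earlier trial using a plaque reduction assay and a non-optimised HTNV plasmid, so they are a range and not a prediction. Rates of 10% to 30% are added to represent early time points, for which the documents give no rates.
- Response q in the two groups not given the antigen: not in the documents. Assumed 0, then varied.

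**Why the test rejects.** Take six groups of n. Four share an observed rate r and two have no responders, so the overall rate is 2r/3. The Pearson statistic is then

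X² = n[4(r/3)² + 2(2r/3)²] / [(2r/3)(1 − 2r/3)] = 6nr/(3 − 2r), on 5 df, critical value 11.07.

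With n = 12:
- 8/12 in each recipient group: 48/1.667 = 28.8, significant.
- 5/12: 30/2.167 = 13.8, significant.
- 3/12: 18/2.5 = 7.2, not significant.

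In all three cases the four recipient groups are identical, so a test among them gives X² = 0. The six-group result reflects only who was given the antigen and how high the response is.

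**Rejection rates.** Simulated, virus-specific outcome, no route or combination effect, q = 0, chi-squared:

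| Response p | 10 per group | 12 per group | Group 6 = 22 |
|---|---|---|---|
| 10% | 10% | 13% | 10% |
| 20% | 25% | 31% | 30% |
| 30% | 55% | 68% | 68% |
| 44% | 92% | 98% | 99% |
| 68% or 78% | 100% | 100% | 100% |

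The exact test is broadly similar and is higher in the middle of the range (78% against 68% at p = 30% with 12 per group). At Day 0 all subjects are seronegative by eligibility, so the test cannot be significant.

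**Cross-reaction** (12 per group, chi-squared). With q = 10%, rejection is a little over 60% at p = 44% and 99% at p = 68%. With q = 20% it is 27% and 89%.

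**Restricted to the four recipient groups**, equal true rates of 30% to 90%: 2.0% to 5.3% across all three size patterns and both tests.

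**Either-virus outcome.** Every group now has a relevant vaccine, and if all six true rates are equal the test rejects in 4% to 5% of trials. But a combination recipient has two ways to respond. With independent responses and no interference, a single-antigen rate p becomes 1 − (1 − p)²: 44% becomes 68.6%, 68% becomes 89.8%, 78% becomes 95.2%. The test then rejects in 20% to 29% of trials with 12 per group. If the HTNV and PUUV rates also differ, from 68% v 78% to 44% v 78%, it rejects in about 29% to 77%. None of this requires a route effect or interference.

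**Each group scored on its own antigen.** The test then compares HTNV response with PUUV response, which is not an objective. At the earlier trial's 68% v 78% it rejects in about 8%.

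**The case against.** The strongest reply is that the objectives do not rest on this test. Table 4.3 lists seven pairwise Fisher tests: 1 v 2, 3 v 4 and 5 v 6 for route, and 1 v 5, 3 v 5, 2 v 6 and 4 v 6 for combination against single vaccine. Every pair shares an antigen. This stands for ever seroconverting, where the relevant contrasts sit directly below the six-group row. It does not cover seropositivity by time point. The four combination pairs also need a statement of which virus's titre counts, since the either-virus problem above applies to them too.

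A second reply is that the virus-specific reading is not written in the SAP. That is correct, so the large rejection rates are conditional on it. The other readings bring the rate down without making the six-group test answer either secondary objective.

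A third is that SAP 5 calls all analyses exploratory and Protocol 11.2 says the study is not designed to show significant group differences. That stands, and it limits the severity.

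A reader might infer that the test is almost sure to be significant for every binary outcome. The documents do not support that. It cannot be significant at Day 0, it rejects in only 10% to 13% of trials at 10% response, and the rate of cross-reaction is unknown. A reader might also take the six-group p-value to be the main immunogenicity result. Nothing in the SAP gives it that priority, and no decision depends on it.

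**Conclusion.** The point holds as a minor one, in conditional form. If the binary outcomes are virus-specific, the all-group test confounds receipt of the antigen with route and combination. With no true effect of either, no cross-reaction and 10 to 12 per group, chi-squared rejects in about 92% to 100% of trials at 44% to 78% response and about 10% to 68% at 10% to 30% response. It rejects less with cross-reaction (27% at 44% v 20%, 12 per group). Restricting it to the four recipient groups brings this to about 5% or lower. On an either-virus reading the size is smaller, but the test still isolates neither question. The figures rest on an assumed cross-reaction rate and on response rates from an earlier trial with a different assay.

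**What to change.** In SAP 9, state that seropositivity and seroconversion are analysed separately for HTNV and PUUV. Replace the association sentence with wording such as: for each virus, association with group is tested only among the groups given that antigen (HTNV: Groups 1, 2, 5 and 6; PUUV: Groups 3, 4, 5 and 6), at post-vaccination time points, using an exact (Fisher-Freeman-Halton) test. Split Tables 3.1, 3.2 and 4.3 by virus. In Table 4.3 remove the six-group p-value and keep the seven pairs, each scored on an antigen that both groups received.

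The cost is a short SAP edit and three table shells. No new data or assays are needed, because every serum is already to be screened for both viruses.

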The rationale for dosages and plan of routes of IM compared to ID administration in the current Phase 1 study is based on prior work by the delivery device manufacturer (Ichor Medical Systems) and prior experience from the previous HTNV DNA and PUUV DNA vaccine clinical study in which candidate vaccines were shown to elicit antibodies in humans when administered by IM EP. This study affords the opportunity to compare the IM and ID routes of administration, at the highest possible doses, given the limitations of the volumes that can be administered by the IM and ID routes (1 mL and 0.2 mL, respectively). This study is being performed to determine which of IM or ID elicits a superior immune response, given the amount of DNA administered using these routes.

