11.2. Planned Enrollment and Reason for Sample Size

The study will enroll 6 randomized groups of 12 subjects each, for a total of 72 subjects. Due to COVID restrictions, 10 subjects from Group 6 may be replaced to ensure completion of the 3 series dose of vaccine. This will account for a total of 82 subjects. This approach will ensure at least 60 subjects complete all vaccinations at around 10 subjects per group, taking possible attrition into account. Subjects will receive one dose of vaccine on Days 0, 28, and 56 and will be followed until Day 220.

The proposed study size is appropriate for a Phase 1 study. A Phase 1 study is designed to evaluate preliminary human safety data but not designed to show statistically significant differences between the groups.

Thus at least 7/10 or 8.4/12 subjects must seroconvert to establish a true seroconversion rate of no less than 30% with 95% confidence.

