% Reporting	xx	xx	xx	xx	xx	xx	x
(95% CI)	(x,x)	(x,x)	(x,x)	(x,x)	(x,x)	(x,x)	
Pair 1	•	•					x
Pair 2			•	•			x
Pair 3					•	•	x
Pair 4	•				•		x
Pair 5			•		•		x
Pair 6		•				•	x
Pair 7				•		•	x

¹P-value obtained from a two-sided Fisher's exact test

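### GMT is a named criterion for the most immunogenic vaccine and route, but the SAP plans no between-group GMT contrast and no confidence interval for any between-group difference

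*SAP*

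**What the plan says.** **Objectives.** Protocol 5.2 and SAP 3.2 ask how the combination compares with the monovalent vaccines, and which combination and route "elicits the most immunogenic response as determined by seroconversion and seropositivity rates, and geometric mean titers (GMT) as measured by PsVNA50". Protocol 4.2 adds: "This study is being performed to determine which of IM or ID elicits a superior immune response".

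**Planned tests.** SAP 9 has two. A chi-squared or Fisher's "exact test will be used to examine the association between group and each binary outcome of interest". For pairs, Fisher's "exact test will be used to examine the difference in the proportion of participants to ever seroconvert between each two groups". The shell for the latter (SAP Appendix I, Table 4.3) shows each group's percentage with a 95% CI and then seven pairs, each with a single p-value "obtained from a two-sided Fisher" exact test.

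**Planned estimates.** All are within group. For proportions: "For each study group, a binomial proportion, and corresponding 95% CI will be calculated". For titers: "The secondary analysis variable is geometric mean titers, with 95% CIs, of the PsVNA50 for HTNV and PUUV specific antibodies", shown in Table 3.4 and Figure 1.5. SAP 9 and Protocol 9 and 11 contain no GMT ratio, titer test or titer model. The analysis of variance in Protocol 11.1.1 covers vital signs and weight.

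**Status.** Protocol 11.2 says a Phase 1 study is "not designed to show statistically significant differences between the groups". SAP 5 calls all analyses exploratory and disclaims power for group differences. Protocol 11.3 sets two-tailed alpha at 0.05.

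**The concern.** The objectives ask comparative questions on three criteria. Two of them (seroconversion and seropositivity) are compared between groups by test only. The third, GMT, is not compared at all. No pair receives an effect estimate with an interval.

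A study not sized for significance testing is best reported by estimates with intervals, yet a p-value is the only pairwise inferential output planned. If most p-values exceed 0.05, the statements about route and about interference between the two vaccines will rest on reading separate group summaries by eye. The titer, which carries more information than the 1:40 cut, would contribute no formal comparison.

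**Working it through.** **1. The plan's own figure.** Protocol 11.2 says 7/10 or 8.4/12 seroconverters establish a true rate of at least 30% with 95% confidence. The exact two-sided 95% lower limit is 34.8% for 7/10 (26.2% for 6/10) and 34.9% for 8/12 (27.7% for 7/12). So 7/10 reproduces, and 8.4 is 0.7 × 12, where the smallest whole count is 8. The figure concerns one group. The documents give no between-group figure to reproduce.

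**2. Contrasts planned for each named criterion.**

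| Criterion | Within-group estimate | Between-group test | Between-group estimate with CI |
|---|---|---|---|
| Seroconversion | yes | Fisher, 7 pairs | none |
| Seropositivity | yes | chi-squared or Fisher | none |
| GMT | yes | none | none |

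**3. Power of the pairwise Fisher test.** Inputs: two-sided 0.05 (Protocol 11.3); 12 enrolled and about 10 completing per group (Protocol 11.2); 22 in Group 6 (Protocol 6.3.1). Power = Σᵢ Σⱼ Bin(i; n₁, p₁) · Bin(j; n₂, p₂) · 1[Fisher p(i, j) ≤ 0.05], summed over all tables.

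| True rates | 10 v 10 | 12 v 12 | 12 v 22 |
|---|---|---|---|
| 68% v 44% | 8% | 13% | 18% |
| 78% v 44% | 17% | 28% | 37% |
| 90% v 50% | 30% | 43% | 56% |
| 90% v 40% | 47% | 64% | 79% |
| 90% v 30% | 67% | 83% | 93% |
| 100% v 50% | 62% | 81% | 97% |

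The 68%, 78% and 44% are rates from the earlier Phase 1 study (Protocol 4.4.2.1.1) and serve only as illustrations. The other rates are hypothetical. The 12 v 22 column assumes that all 22 Group 6 subjects are evaluable, which is optimistic because ten of them are replacements for subjects whose data were impaired.

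The higher rate at which power first reaches 50%, by lower rate:

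| Lower rate | 12 v 12 | 10 v 10 |
|---|---|---|
| 10% | 54% (gap 44) | 62% (gap 52) |
| 30% | 76% (gap 46) | 84% (gap 54) |
| 50% | 93% (gap 43) | 97% (gap 47) |

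Hence about 40 to 55 points. In observed counts at 12 per group, 9/12 is significant only against 3/12 or fewer.

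**4. What an interval adds.** The Newcombe limits are d − √[(p₁−l₁)² + (u₂−p₂)²] and d + √[(u₁−p₁)² + (p₂−l₂)²], with Wilson limits l and u.
- 9/12 v 5/12: Wilson limits 46.8–91.1% and 19.3–68.0%; d = +33 points, 95% CI −5 to +61. Fisher alone prints p = 0.21.
- 9/12 v 9/12: d = 0, 95% CI −32.5 to +32.5. Fisher alone prints p = 1.0.

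**5. Cost of the 1:40 cut, one draw, 12 v 12.** Assumptions, none from the documents: lognormal titers, log10 SD 0.5, 0.6 or 0.7, a true ratio of 4 (0.602 in log10), and 70% at or above 1:40 in the better group. The other group's share is then Φ(0.524 − 0.602/SD) = 25%, 32% or 37%. Values below 20 are set to 14.1, as in SAP 9. Power from 20,000 simulated trials:

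| log10 SD | Fisher at 1:40 | Wilcoxon | Welch t, log titer |
|---|---|---|---|
| 0.5 | 50% | 75% | 77% |
| 0.6 | 35% | 58% | 60% |
| 0.7 | 26% | 46% | 48% |

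Information kept by the cut is roughly [(1.96 + z_Fisher)/(1.96 + z_Welch)]², where z is the normal quantile of the power. At SD 0.5 this is (1.97/2.69)² = 54%; at SD 0.7, (1.33/1.92)² = 48%. About half is kept, and part of the loss is Fisher's conservatism: its actual size at 10 to 12 per group is 0.9% to 2.3% when both rates are 50% or both 78%.

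**6. Precision of a GMT ratio.** Before censoring, the 95% CI factor is 10^(t₀.₉₇₅,₂₂ · SD · √(2/12)). SD 0.5: 10^(2.074 × 0.5 × 0.408) = 2.65. SD 0.7: 3.91. With 14.1 substituted below 20, under the model of step 5, a true ratio of 4 is estimated near 3 and the nominal 95% Welch interval covers the truth 89–91% of the time. A ratio based on substitution should therefore not be the main estimate.

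**The case against.** The study is openly exploratory, its limited power is disclosed, and the first secondary objective asks only for a preliminary assessment. Table 4.3 prints group percentages with CIs, and Table 3.4 and Figure 1.5 show GMTs by group, so point differences and ratios can be read off. All of this stands. What is missing is an interval on the contrast, which two separate group intervals do not supply.

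Stronger readings are tempting, and the documents do not support them:
- *A reader might infer that the plan yields no difference whatever the truth.* It does not: power at 12 v 12 is 83% for 90% v 30% and 81% for 100% v 50%.
- *A reader might infer that p-values are all the plan reports.* Group estimates with CIs are planned.
- *A reader might infer that the plan treats p > 0.05 as similarity.* No text says so. The risk lies in later interpretation.
- *A reader might take 68% v 44% as the expected effect here.* Those rates come from a plaque reduction test, an HTNV plasmid that was not codon-optimised, and a combination with half the dose of each plasmid. Protocol 4.2 reports that the optimised plasmid overcame the interference.
- *A reader might take step 5 as the power of the planned test.* It cuts one draw, whereas Table 4.3 uses ever seroconverted across draws.

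**Conclusion.** The point holds as a gap between objective and analysis. GMT has no planned between-group contrast, and no pair has a difference with a CI. A non-significant Fisher result is more likely than not unless the true gap in seroconversion exceeds about 40 points at 12 per group or about 55 at 10. That threshold is exact arithmetic from the stated group sizes and alpha. The size of the gain from analysing titers (power of 77% to 48% instead of 50% to 26%) rests on the assumed SDs, lognormal titers and a single draw. The change is well worth making because it is cheap and matches the stated objective. It makes the imprecision visible and uses the titers, but it does not turn a study of this size into a decisive comparison.

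**What to change.** In SAP 9 and Appendix I:

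1. Add a table for the seven Table 4.3 pairs, per virus and only in groups given that antigen: six pairs with one virus each and Group 5 v 6 with both, so eight contrasts. Report the Day 84 GMT ratio with 95% CI from a censored lognormal (Tobit) model that treats titers below 20 as left-censored. State in advance what is reported if nearly all of a group is below 20. Day 84 is 84 − 56 = 28 days after dose 3, and Protocol 4.4.2.1.1 places peak titers generally within a month of the last dose.
2. As sensitivity analyses, give the Welch analysis of log10 titers with 14.1 substituted, noting its bias toward 1, and a Wilcoxon test.
3. In Table 4.3, print the risk difference with 95% CI (for example Newcombe) beside each Fisher p-value.
4. Base the statements on the most immunogenic option and on the combination relative to monovalent on these estimates, and say that p > 0.05 will not be reported as similarity.
5. Mark the non-concurrent contrasts. By Protocol Appendix B, Groups 2 and 4 were enrolled by March 2020, while Groups 1 and 3 were to follow from November 2021. Both monovalent route comparisons (1 v 2 and 3 v 4) are therefore non-concurrent, and those involving Group 6 are partly so.

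Cost: SAP wording, one added table and one extended table; no new subjects or blood. Downsides: one time point is named as the main one, and the GMT ratio intervals will be wide, a factor of roughly 2.7 to 3.9 either way at 12 per group before censoring.
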